8.8 Pharmacokinetics and Pharmacodynamics

Pharmacokinetics/pharmacodynamics will be analyzed on PK Analysis Set. The Nektar Therapeutics Pharmacology group will estimate PK parameters and analyze PK/PD data. Detailed descriptions of PK analysis will be included in a PK analysis plan developed separately.

8.9 Handling of Multiplicity

No corrections for multiplicity will be made.

8.10 Handling Missing Values

No other missing data imputation will be performed unless otherwise stated in this document.

9.0 CHANGES OF ANALYSIS FROM PROTOCOL

Not applicable.

General disorders and administration site conditions	General system disorders NEC	Asthenic conditions	Sluggishness
Nervous system disorder	Neurological disorders NEC	Disturbances in consciousness NEC	Somnolence

Abuse potential adverse event terms of interest characterized as psychotomimetic in nature

System Organ Class	Higher Level GT	Higher Level Term	Preferred term
Psychiatric disorders	Psychiatric and behavioural symptoms NEC Psychiatric disorders	Abnormal behaviour NEC	Abnormal behaviour
Nervous system disorders	Sleep disturbances (incl subtypes)	Abnormal sleep-related events	Abnormal dreams
Psychiatric disorders	Schizophrenia and other psychotic disorders	Psychotic disorder NEC	Acute psychosis
	Mood disorders and disturbances NEC	Emotional and mood disturbances NEC	Anger
	Anxiety disorders and symptoms	Anxiety symptoms	Agitation
	Deliria (incl confusion)	Confusion and disorientation	Confusional state
	Communication disorders and disturbances	Communications disorders	Communication disorder
	Deliria (incl confusion)	Deliria	Delirium
	Disturbances in thinking and perception	Delusional symptoms	Delusion
	Schizophrenia and other psychotic disorders	Delusional disorders	Delusional disorder, unspecified type
	Dissociative disorders	Dissociative states	Depersonalisation
	Disturbances in thinking and perception	Perception disturbances	Derealisation
	Deliria (incl confusion)	Confusion and disorientation	Disorientation
	Dissociative disorders	Dissociative states	Dissociation
			Dissociative disorder
	Cognitive and attention disorders and disturbances	Cognitive and attention disorders and disturbances NEC	Disturbance in attention
Nervous system disorders	Dissociative disorders	Dissociative states	Dysarthria
Psychiatric disorders	Mood disorders and disturbances NEC	Emotional and mood disturbances NEC	Emotional disorder
Psychiatric disorders	Anxiety disorders and symptoms	Fear symptoms and phobic disorders (incl social phobia)	Fear
		Perception disturbances	Flashback

System Organ Class	Higher Level GT	Higher Level Term	Preferred term
	Disturbances in thinking and perception	Thinking disturbances	Flight of ideas
		Perception disturbances	Hallucination
			Hallucination, auditory
			Hallucinations, mixed
			Hallucination, olfactory
			Hallucination, synaesthetic
			Hallucination, tactile
	Hallucination, visual		
Personality disorders and disturbances in behaviour	Behaviour and socialisation disturbances	Hostility	
Nervous system disorders	Neurological disorders NEC	Paraesthesias and dysaesthesias	Hypoaesthesia
Psychiatric disorders	Disturbances in thinking and perception	Perception disturbances	Illusion
	Personality disorders and disturbances in behaviour	Behaviour and socialisation disturbances	Indifference
	Mood disorders and disturbances NEC	Emotional and mood disturbances NEC	Irritability
	Dementia and amnesic conditions	Amnesic symptoms	Memory impairment
	Cognitive and attention disorders and disturbances	Cognitive and attention disorders and disturbances NEC	Mental impairment
	Mood disorders and disturbances NEC	Fluctuating mood symptoms	Mood swings
Musculoskeletal and connective tissue disorders	Muscle disorders	Muscle tone abnormalities	Muscle rigidity
Psychiatric disorders	Sleep disorders and disturbances	Parasomnias	Nightmare
Nervous system disorders	Neurological disorders NEC	Paraesthesias and dysaesthesias	Paraesthesia
Psychiatric disorders	Personality disorders and disturbances in behaviour	Behaviour and socialisation disturbances	Paranoia

System Organ Class	Higher Level GT	Higher Level Term	Preferred term
	Schizophrenia and other psychotic disorders	Psychotic disorder NEC	Psychotic disorder
Nervous system disorders	Neurological disorders NEC	Sensory abnormalities NEC	Sensory disturbance
Psychiatric disorders	Disturbances in thinking and perception	Delusional symptoms	Somatic delusion
		Perception disturbances	Somatic hallucination
	Psychiatric and behavioural symptoms NEC	Abnormal behaviour NEC	Staring
	Sleep disorders and disturbances	Dyssomnias	Stupor
	Disturbances in thinking and perception	Thinking disturbances	Thinking abnormal
			Thought blocking
Schizophrenia and other psychotic disorders	Brief psychotic disorder	Transient psychosis	

***Drug Withdrawal- Related Adverse Events Occurring Following Drug Discontinuation
 (Preferred Terms; MedDRA 18.0)***

System Organ Class	Preferred term
Cardiac disorders	Syncope
Gastrointestinal disorders	Vomiting
	Diarrhoea
	Nausea
General disorders and administration site conditions	Hyperhidrosis
	Pain
Musculoskeletal and connective tissue disorders	Chills
Nervous system disorders	Headache
	Agitation
	Dyssomnia
	Insomnia
	Poor quality sleep
	Syncope
	Terminal insomnia (lower level term of interest: early morning awakening)
	Tremor
Psychiatric disorders	Agitation
	Anhedonia
	Anxiety
	Dysphoria
	Dyssomnia
	Dysthymic disorder
	Feeling of despair
	Insomnia
	Morose
	Negative thoughts
	Nervousness

1.0 INTRODUCTION

NKTR-181 is a new molecular entity (NME) opioid analgesic designed with the intent of preserving opioid analgesic effectiveness, while reducing the rate and extent of entry of the molecule into the CNS, and thereby reducing CNS-related side effects.

The intent of this document is to provide guidance for the PK analysis of data captured according to protocol number 14-181-08, “A Phase 3 Multicenter, Open-Label, 52-Week Study to Evaluate the Long-Term Safety and Tolerability of NKTR-181 in Subjects with Moderate to Severe Chronic Low Back Pain or Chronic Non-cancer Pain”. This PK analysis plan (PKAP) describes the planned analysis of the PK data and the description of the tables, listings, and figures (TLFs) to be presented in the Clinical Study Report (CSR). A separate statistical analysis plan provides the description of the planned statistical analyses to support the primary and secondary objectives of the study.

This PKAP extends and supersedes the descriptions of PK analyses provided in the protocol; any substantially different analysis will be identified in the CSR. Should additional analyses beyond those described in the PKAP be required, they may be performed and will be identified in the appropriate section of the CSR. Deviations from this PKAP, both substantial and non-substantial, will be documented in the CSR.

2.0 STUDY OBJECTIVES

2.1 Primary Objective

The primary objective of the study is to evaluate the long-term safety and tolerability of NKTR-181 in subjects with moderate to severe chronic low back pain or chronic non-cancer pain.

2.2 Secondary Objectives

The secondary objective of the study is to evaluate the effectiveness of NKTR-181 as measured by the modified Brief Pain Inventory-Short Form (mBPI-SF).

2.3 Objective of the Pharmacokinetic Analysis

To characterize the pharmacokinetics of NKTR-181 and its metabolites oxycodol and oxycodone in subjects enrolled in the PK sub-study using noncompartmental analysis.

To evaluate NKTR-181 pharmacokinetics using sparse samples collected in subjects enrolled in the study.

3.0 STUDY DESIGN

3.1 General Description

This is a multicenter, Phase 3, open-label safety and tolerability study in which approximately 600 subjects will receive open-label NKTR-181 for up to 12 months (52 weeks) from approximately 100 sites. Study may include newly enrolled subjects (approximately 250 De Novo Subjects) and subjects who have recently completed Study 14-181-07 (Rollover Subjects).

The study comprises 3 periods:

Screening: Up to 21 days; Visits 1-2

Treatment: 52 weeks; Visits 3-22

Safety Follow-Up: Approximately 14 days after the last dose of study drug; Visits 23-24

The three study periods are described in further detail in Study Protocol 14-181-08, Sections 6.1 to 6.3. A schematic of the study design is presented in Section 1.1, and the Schedule of Assessments is presented in Section 1.2 of the protocol.

3.2 Pharmacokinetic Assessment

This study will investigate the PK of NKTR-181 in patients with chronic low back pain or chronic non-cancer pain. Sparse blood samples for PK analysis will be collected from all subjects at follows: Visits 3, 4, 5, 6, 7, 8, 9, 10, 11, 12, 13, 17, 20, 21, 22, Unscheduled visits, end of treatment, and Early Termination visits.

In addition, a subset of approximately 100 subjects will be participating in the PK sub-study. The PK sub-study commences after a stable dose has been identified. This may occur as early as the second visit following the start of the Treatment phase. The PK collection visit will be scheduled to start in the morning, prior to the subject taking their morning dose of NKTR-181. Subjects should be reminded in advance of the visit to hold their morning dose of study drug and to bring their study drug supply to the clinic with them. Subjects will take their morning dose of NKTR-181 in the clinic after a predose PK sample is drawn. PK samples will be obtained 0.5, 1, 2, 3, 4, 5, 6, 8, and 12 hours postdoc.

4.0 PHARMACOKINETIC ENDPOINTS

4.1 Pharmacokinetic Endpoints for the PK Sub-study

The endpoints for PK analyses include non-compartmental PK parameters derived from plasma NKTR-181, oxycodol, and oxycodone concentration data.

Where possible, the following plasma PK parameters will be calculated for all three analytes:

C_{max} : Maximum observed plasma concentration expressed in units of ng/mL.

T_{max} : Time that C_{max} was observed expressed in units of hr.

$AUC_{(0-last)}$: Area under the plasma concentration-time curve from time =0 to the time of the last measureable concentration. $AUC_{(0-last)}$ will be expressed in units of ng.hr/mL.

$AUC_{(0-12)}$: Area under the plasma concentration-time curve from time =0 to the time of the last time-point (12 hour post morning dose). $AUC_{(0-12)}$ will be expressed in units of ng.hr/mL.

Dose normalized C_{max} : Dose normalized maximum observed plasma concentration expressed in units of ng/mL/mg.

Dose normalized $AUC_{(0-last)}$: Dose normalized area under the plasma concentration-time curve expressed in units of ng.hr/mL/mg.

Metabolite to parent ratio for $AUC_{(0-last)}$ ($M/P_{AUC(0-last)}$) calculated as:

$$(AUC_{(0-last)metab} * MW_{parent}) / (AUC_{(0-last)parent} * MW_{metab})$$

Metabolite to parent ratio for C_{max} (M/P_{Cmax}) calculated as:

$$(C_{max\ metab} * MW_{parent}) / (C_{max\ parent} * MW_{metab})$$

Molecular Weight (MW) Table:

Analyte	Molecular Weight (g/mol)
NKTR-181 (parent)	595.72
Oxycodol (metabolite)	317.38
Oxycodone (metabolite)	315.36

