8.1 Pharmacokinetic Blood Sample Collection

Blood samples for PK analysis will be collected from all subjects according to the Schedule of Assessments (Section 1.2). Each participating site will be provided instructions for specimen collection, processing, storage, packaging, and shipment. **The first PK blood sample must be collected from all subjects prior to receiving the first dose of study drug (Visit 3).**

In a PK substudy of approximately 100 subjects at selected sites, serial blood samples will also be collected during a complete 12-hour dosing interval as shown in [Table 2](#).

Table 2: Pharmacokinetic Sample Collection Times in the PK Substudy

Time (hours)	Event ^a	Sample Name	Actual Time (example)
Predose	Cryovial Preparation		Approximately 15 - 30 min
Predose	Sample collection	Predose	Within 15 mins prior to dosing
0:00	NKTR-181 dosing		9:00 AM
0:30	Sample collection	0.5 hour postdose	9:30 AM
1:00	Sample collection	1.0 hour postdose	10:00 AM
2:00	Sample collection	2.0 hours postdose	11:00 AM
3:00	Sample collection	3.0 hours postdose	12:00 PM
4:00	Sample collection	4.0 hours postdose	1:00 PM
5:00	Sample collection	5.0 hours postdose	2:00 PM
6:00	Sample collection	6.0 hours postdose	3:00 PM
8:00	Sample collection	8.0 hours postdose	5:00 PM
12:00	Sample collection	12.0 hours postdose	9:00 PM

^a Cryovials for PK sample collection must be prepared in advance of the first sample collection time on the day of collection and must undergo processing steps following sample collection according to the instructions provided in the Laboratory Manual.

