5.0 PK ANALYSIS POPULATION

5.1 PK Sub-Study Population

The PK sub-study population included all subjects in the PK subgroup who received NKTR-181 and had relatively complete individual analyte concentration-time profiles that allow computation of meaningful PK parameter values. Subjects with pre-dose BLQ levels in the PK sub-study population will be excluded from the descriptive summary tables. The number and % of subjects with pre-dose BLQ samples will be tabulated by dose level and overall.

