6.0 PHARMACOKINETIC DATA EVALUATION

6.1 Bioanalysis of Plasma Samples

Concentrations of NKTR-181, oxycodol, and oxycodone in plasma samples will be assayed using validated methods. NKTR-181 levels will be analyzed for both spare samples and PK subgroup samples. Oxycodol and oxycodone levels will be analyzed for the PK subgroup samples only.

For the purpose of the PK analysis, plasma concentration values reported as below the limit of quantification (BLQ) will be treated as zero for pre-dose samples. Plasma concentrations values reported as BLQ at all other times will be considered as missing. Concentration values in any sample matrix reported as NR (not received) or NA (not analyzed) will be treated as missing values.

Unreliable results, such as those arising from procedural errors during conduct of the study or analytical errors will not be used.

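### Dose-normalised AUC and the metabolite-to-parent AUC ratio are built on AUC(0-last), so a missed 12-hour draw shortens the interval; the planned AUC(0-12) would fix it

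*SAP*

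**What the plan says.** The PKAP is bound with the SAP and numbered separately; section numbers below are the PKAP's unless the protocol is named.

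- **Two areas are planned.** Section 4.1 defines AUC(0-last) as "Area under the plasma concentration-time curve from time =0 to the time of the last measureable concentration", and AUC(0-12) as the area to the fixed time point 12 hours after the morning dose. Both are to be calculated, where possible, for NKTR-181, oxycodol and oxycodone.
- **Only one feeds the derived measures.** Dose-normalised AUC ("Dose normalized area under the plasma concentration-time curve expressed in units of ng.hr/mL/mg") is listed for AUC(0-last). The AUC-based metabolite-to-parent ratio has AUC(0-last) in both numerator and denominator, with a molecular-weight correction. No AUC(0-12) version of either is listed. A ratio based on Cmax is also planned.
- **Sampling.** Protocol 8.1, Table 2, and PKAP 3.2 take samples predose and at 0.5, 1, 2, 3, 4, 5, 6, 8 and 12 h. The last is the "12.0 hours postdose" sample, at 9 PM in the Table 2 example. Nothing is drawn between 8 and 12 h.
- **Who is included.** Section 5.1 keeps sub-study subjects who "had relatively complete individual analyte concentration-time profiles" and whose data allow meaningful parameters. It removes subjects with pre-dose BLQ levels from the summary tables, without naming the analyte.
- **Data rules.** Section 6.1 states: "Plasma concentrations values reported as BLQ at all other times will be considered as missing". Section 6.2 uses actual sampling times and the linear trapezoidal rule, with no extrapolation.

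**The concern.** On a stable twice-daily dose, exposure is the area over the whole dosing interval, and the sub-study was designed to sample that interval. AUC(0-last) equals that area only when the 12-hour concentration is present and measurable. Otherwise it stops at 8 h or earlier, while the dose it is divided by stays the same.

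Two mechanisms can shorten it, and they act differently:

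- **A missed 12-hour draw** shortens all three analytes together. It lowers dose-normalised AUC directly.
- **A BLQ 12-hour value in one analyte** shortens that analyte only. The ratio then divides areas over different intervals.

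At stake is whether the by-dose summaries of two descriptive exposure measures compare like with like.

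**Working it through.** The plan states no figure on this point, so there is none to reproduce. The check traces the rules, then sizes the effect under stated assumptions.

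**1. Following the rules with no 12-hour sample.** Section 5.1 does not require that sample, so the subject can stay in. Section 6.2 does not extrapolate. AUC(0-last) then equals AUC(0-8), and dose-normalised AUC is AUC(0-8)/dose.

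**2. Size for a missed draw.** Assumed, because the documents give neither: half-life 4 to 16 h, Tmax parameter 2 to 3 h. The model is one-compartment oral dosing at steady state with τ = 12 h:

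C(t) ∝ ka/(ka − ke) × [e^(−ke·t)/(1 − e^(−ke·τ)) − e^(−ka·t)/(1 − e^(−ka·τ))]

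Here ke = ln 2 / half-life, and ka solves ln(ka/ke)/(ka − ke) = Tmax. The linear trapezoid is applied on the protocol's sampling times; areas are in relative units.

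| Half-life, Tmax | ke, ka (per h) | AUC(0-8) | AUC(0-12) | AUC(0-8)/AUC(0-12) | Loss |
|---|---|---|---|---|---|
| 4 h, 2 h | 0.173, 1.095 | 4.756 | 5.774 | 0.824 | 18% |
| 16 h, 3 h | 0.043, 1.131 | 16.379 | 23.056 | 0.710 | 29% |

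A wider assumed range (half-life 2 to 24 h, ka 0.5 to 2 per h) gives losses of about 7% to 31%. A perfectly flat profile gives 1 − 8/12 = 33%.

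**3. Effect on the ratio.** Assumed: half-life 4 to 12 h for each analyte, ka 1 per h for the parent and 0.5 per h for the metabolite. The fractional loss from stopping at 8 h is then 0.179 to 0.277 for the parent (Lp) and 0.216 to 0.293 for the metabolite (Lm).

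- Both stop at 8 h (missed draw): the change is (1 − Lm)/(1 − Lp) − 1. The extremes are 0.707/0.821 − 1 = −14% and 0.784/0.723 − 1 = about +8% to +9%, depending on rounding. The intervals still match, so the shift is modest and can go either way.
- Only the metabolite stops at 8 h: −Lm, so 22% to 29% too low.
- Only the parent stops at 8 h: 1/(1 − Lp) − 1, so 22% to 38% too high.

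The molecular-weight factors, 595.72/317.38 = 1.877 and 595.72/315.36 = 1.889, are constants and play no part.

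**4. How far the pre-dose BLQ exclusion helps.** In the steady-state model C(0) = C(12) exactly. An analyte that is BLQ at 12 h would therefore be expected to be BLQ predose. If the exclusion is applied to each analyte, it takes most of the one-analyte cases in step 3 out of the summary tables. It does nothing for a missed draw.

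**5. With AUC(0-12).** Every contributing subject and analyte covers the same nominal 0 to 12 h, so the mismatch disappears by construction. If every 12-hour value is measurable, AUC(0-last) equals AUC(0-12) and nothing changes.

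**The case against.** The case for leaving the text alone is substantial.

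- **The fixed-interval area is already reported.** AUC(0-12) is planned for all three analytes, and section 6.3.1 lists parameters by subject and summarises them by dose level. A reader could divide the listed values. The Cmax ratio does not depend on the AUC interval. This stands, and it limits the harm; it does not explain why the two planned summaries use the variable interval.
- **No decision rests on these measures.** The PK objective in section 2.3 is to characterise pharmacokinetics. The PKAP states no dose-proportionality objective or test, and exposure-response work goes to a separate population PK analysis. This stands.
- **Frequency is unknown.** The documents give no rate of missing or BLQ 12-hour samples, and they do not say that a profile without that sample counts as sufficiently complete. This stands; equally, section 5.1 does not exclude such a profile.
- **The remedy can select.** Omitting analytes that are BLQ at 12 h can remove the lowest exposures. This stands, and is why the omissions should be counted and reported.

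Two stronger readings are tempting, and the documents support neither.

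- **Truncation at low doses mimics greater-than-proportional exposure.** The 18-29% loss comes from a missed draw, and nothing suggests that missed draws depend on dose. BLQ truncation could depend on dose, but there the pre-dose exclusion applies and the late area lost is smallest.
- **The metabolite ratio could fall by 32-45%.** This takes a metabolite last measurable at 6 h, where the step 2 model gives AUC(0-6)/AUC(0-12) of 0.546 to 0.682. In the 45% case the 6 h, 8 h and predose levels are 88%, 81% and 68% of peak. The quantification limit would have to lie between 81% and 88% of peak, so the predose sample would be BLQ too and the subject excluded if the rule covers that analyte.

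**Conclusion.** The point holds in a limited form. As written, a subject without a 12-hour draw can enter the dose-normalised AUC summary about 18-29% too low, under the assumed half-life and Tmax ranges. That is a per-subject figure; the effect on any dose-level summary cannot be computed from the documents.

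For the AUC ratio, the exposure is mainly to one analyte being BLQ at 12 h. How much of that remains depends on whether the section 5.1 exclusion is applied to each analyte, which the text leaves open. No dose-proportionality bias is shown. The Cmax ratio and the primary safety objective are untouched. This is a cheap improvement to descriptive endpoints in a sub-study of about 100 subjects.

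**What to change.** - In PKAP 4.1, define dose-normalised AUC and the AUC-based metabolite-to-parent ratio on AUC(0-12) for all three analytes.
- Derive AUC(0-12) only where a 12-hour concentration, drawn before the next dose, is available for that analyte. Otherwise list the subject and omit them from those two summaries.
- Report, by dose level and analyte, how many were omitted and whether the cause was a missed draw or a BLQ value.
- Keep AUC(0-last) as a listed parameter.

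The cost is PKAP wording and one table of counts, using a parameter already planned. Some subjects leave two descriptive summaries. Because BLQ omissions can remove the lowest exposures, the counts should be read alongside those summaries.

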4.2 Pharmacokinetic Evaluation based on Sparse Sampling Data

NKTR-181 concentration-time data at each dose level and study visit during Treatment period will be pooled from all subjects and described by descriptive statistics to evaluate trends in drug concentrations with dose and study visits. No formal statistical tests will be conducted. Furthermore, visual inspection of drug concentrations at each dose level and study visit will be performed. Only patients on a stable dose level will be included in the graphical analysis.

5.0 PK ANALYSIS POPULATION

5.1 PK Sub-Study Population

The PK sub-study population included all subjects in the PK subgroup who received NKTR-181 and had relatively complete individual analyte concentration-time profiles that allow computation of meaningful PK parameter values. Subjects with pre-dose BLQ levels in the PK sub-study population will be excluded from the descriptive summary tables. The number and % of subjects with pre-dose BLQ samples will be tabulated by dose level and overall.

5.2 Sparse Sampling PK Population

Subjects who received at least one dose of NKTR-181 and had at least one plasma sample will be included in the sparse sampling PK population. The PK analysis data set will include all plasma samples from all subjects with the following exceptions: Subjects with only pre-first dose NKTR-181 concentration available for the entire duration of the study and post-dose samples with BLQ concentrations.

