16. De Novo Subject undergoing opioid taper will have COWS administered at Visit 2. All subjects will be administered COWS at Visit 3. COWS score must be ≤ 12 to enter the Treatment Period.
17. De Novo Subjects taking opioid analgesics at Visit 2 will complete a SOWS assessment daily while tapering their opioids over the next 7-14 days. All subjects will complete the SOWS on the two days prior to Visit 21 and daily between Visits 21 and 22. Subjects will then complete the SOWS twice daily for three days following the last dose of study drug (i.e., following Visit 22), then daily for the remainder for the study (i.e., through Visit 24).
18. A PK sample will be collected on all subjects at Visit 3. PK sample at Visit 3 must be collected prior to the subject taking the first dose of study medication for De Novo Subjects.
19. For subjects participating in the PK substudy, the dosing period PK collection may be completed when a stable dose has been identified. This may occur as early as the second visit following the start of a dose level. Subjects will be reminded to *not* take their AM dose on the planned dosing period PK collection visit. A predose sample will be obtained and the subject will take their AM dose in the clinic. PK samples will be obtained 0.5, 1, 2, 3, 4, 5, 6, 8, and 12 hours postdose.
20. Dispense taper study drug only for subjects completing study. Taper study drugs are not dispensed at Early Termination.
21. Study drug is not dispensed at Visit 22/EOT. Final study drug and rescue medication reconciliation conducted at Visit 22/EOT.
22. Collection of concomitant medications and adverse events will start after the signing of the ICF through study completion.

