6.3 Presentation of Individual and Mean Plasma Drug Concentrations and PK Parameters

6.3.1 Listings and Tables

Listings for blood collection dates and times will be generated by subject, and treatment. Sampling time deviations will be computed as differences between scheduled (nominal) and actual sampling times and expressed in minutes and as a percentage of the nominal time.

Plasma analyte concentrations at each nominal PK sampling time will be tabulated by treatment using descriptive statistics, including the number of observations (n), n listed as BLQ, arithmetic mean, geometric mean, standard deviation, standard error of the mean (SEM), CV%, median, minimum and maximum. Missing and BLQ concentration values will be treated using the criteria provided in Section 6.1. Missing concentration values will not be included in the descriptive statistics.

For the PK sub-study, plasma PK parameters will be listed by subjects and summarized by dose level using descriptive statistics, including, n, geometric mean, mean, standard deviation, CV%, median, minimum and maximum.

For sparse PK sampling, number of subjects and samples at each dose level and study visit will be tabulated and summarized using descriptive statistics, including, n, median, and range.

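### As worded, the sparse-PK data set admits the sub-study's serial samples, so a profiled subject can count ten times in one dose-by-visit cell

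*SAP*

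**What the plan says.** The PKAP describes two kinds of blood sample. Section 3.2 says that "Sparse blood samples for PK analysis will be collected from all subjects" at a list of visits; it gives no time after dose for them. It then adds that "a subset of approximately 100 subjects will be participating in the PK sub-study". For those subjects the protocol's Schedule of Assessments (footnote 19) calls for a pre-dose sample, after which "PK samples will be obtained 0.5, 1, 2, 3, 4, 5, 6, 8, and 12 hours postdose". PKAP 6.1 has NKTR-181 assayed in both kinds.

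Membership of the sparse-sampling population (PKAP 5.2) needs one dose and one plasma sample, so sub-study subjects belong to it. The data rule is "The PK analysis data set will include all plasma samples from all subjects with the following exceptions". The exceptions are subjects whose only concentration precedes the first dose, and post-dose samples below the limit of quantification.

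PKAP 4.2 says that concentrations "at each dose level and study visit during Treatment period will be pooled from all subjects" and described so as to look for trends with dose and visit, without formal tests. PKAP 6.3.1 gives the output: "number of subjects and samples at each dose level and study visit will be tabulated and summarized using descriptive statistics, including, n, median, and range". No section limits a subject to one sample per visit.

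**The concern.** The inclusion rule is affirmative and its list of exceptions is closed. A programmer who applies it as written would keep every serial sample. A profiled subject would then have ten rows in the cell for that visit and dose, while each other subject has one. The ten values come from one person over one dosing interval, so they are correlated, and they cover the whole interval whatever the timing of the sparse draws.

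At stake is the comparison that PKAP 4.2 sets up. A cell that contains profiles and a later cell with one value per subject could differ only because they were sampled differently, and the difference could be read as a trend with visit or dose. A count of samples would also suggest more information than the number of subjects supports.

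**Working it through.** The documents give no computed figure on this point, so there is none to reproduce. The check is how much weight the serial samples could carry.

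**Inputs.** About 600 subjects (PKAP 3.1) and about 100 in the sub-study (PKAP 3.2). Samples per profile: 1 pre-dose + 9 post-dose = 10 (protocol 1.2, footnote 19, and Table 2).

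**Assumptions.** No dropout; the same sub-study share at every dose level; one sparse sample from every subject not profiled at that visit; the profile replaces that visit's sparse sample.

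**Share of rows.** If the 100 profiles spread evenly over k visits, s = 100/k subjects are profiled at each, and serial samples make up 10s / (10s + 600 − s) of the rows.

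| k visits | serial rows | other rows | serial share | share with one row per subject |
|---|---|---|---|---|
| 1 | 1000 | 500 | 66.7% | 16.7% |
| 2 | 500 | 550 | 47.6% | 8.3% |
| 3 | 333 | 567 | 37.0% | 5.6% |
| 4 | 250 | 575 | 30.3% | 4.2% |
| 6 | 167 | 583 | 22.2% | 2.8% |

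**When serial rows are a majority.** Let p be the fraction of a cell's subjects who are profiled there. The serial share is 10p / (10p + 1 − p). It exceeds one half when 10p > 1 − p, that is p > 1/11 = 9.1%.

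**Can a cell reach that?** The profile visit is not fixed; it follows each subject's own stable dose (protocol 6.2.1). That argues against all profiles falling at one visit. On the other hand, cells are split by six dose levels as well as by visit. In a cell of ten subjects one profile is enough: 10 / (10 + 9) = 10/19 = 53%. The plots in PKAP 4.2 keep only subjects on a stable dose, which drops titrating subjects from the cell but keeps profiled ones. So p above 9.1% is possible locally, but the documents do not show how often.

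**Effect on the median.** This needs pharmacokinetic values and sparse draw times that the documents do not give. The following is an illustration only. It assumes a one-compartment model at steady state with 12-hour dosing, absorption rate 1/h, half-life 4, 8 or 14 h, and between-subject log-SD 0.5. It uses 600 subjects, 100 of them profiled, in 200 replicates. The shift is against one sample per subject at the sparse draw time; each range runs over the three half-lives.

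| assumed sparse draw time | all profiles at 1 visit | over 3 visits | over 6 visits |
|---|---|---|---|
| spread over 0–12 h | +1.3% to +9.1% | +0.6% to +5.1% | +0.2% to +3.6% |
| 1–5 h post-dose | −8.4% to −19.9% | −4.5% to −10.5% | −3.2% to −6.1% |
| 11–12 h (near trough) | +17.6% to +79.2% | +9.5% to +26.4% | +5.5% to +13.3% |

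The sign changes with the assumed draw time. The size depends on that, on the half-life and on how far the profiles cluster.

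**The case against.** The strongest reply is that the PKAP never meant serial samples to enter. Section 5.2 is headed as the sparse-sampling population. The second PK objective (2.3) is "To evaluate NKTR-181 pharmacokinetics using sparse samples collected in subjects enrolled in the study". Section 3.2 introduces the sub-study as an addition to the sparse draws, 6.1 names the two kinds separately, and 6.3.1 and 6.3.2 give them separate tables and plots. On that reading, the word all in 5.2 means all sparse samples. The reading is available and probably reflects the intent. It does not settle the matter, because the only operative inclusion rule says otherwise and two programmers could build different tables from it. The protocol cannot decide, since PKAP 1.0 says the PKAP supersedes the protocol's PK descriptions.

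A second reply is that little depends on these summaries. That stands in large part. They are descriptive, without tests or confidence intervals, and serve a PK objective but no primary or secondary objective. Section 6.3.1 counts subjects as well as samples, so a surplus of samples would be visible. It does not, however, say whether the median is taken over samples or subjects.

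A reader might infer that serial samples will dominate the medians. The documents do not support that. Under even spread over six visits, 78% of rows come from other subjects. The 67% figure needs all 100 profiles at one visit, which the floating profile visit makes an extreme bound. Even a majority of rows need not move the median far if sparse draws are spread over the interval.

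**Conclusion.** The point holds as a defect of wording with a conditional effect. Read literally, PKAP 5.2 admits the serial samples and gives a profiled subject ten rows against one; other sections suggest that this was not intended. If the rule is applied as written, serial samples are about 22% of rows at a visit under even spread over six visits, and a majority only in cells with more than 9.1% of subjects profiled. These shares rest on the planned 100 of 600, no dropout, and an equal sub-study share across dose levels.

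The medians used for dose and visit trends can be distorted. By how much and in which direction cannot be determined, because the documents give neither the sparse draw times nor the spread of profile visits. It would also go too far to say that an inference is invalidated: none is planned on these data. The change is worth making because it is cheap and removes a possible artefact from one of the two PK objectives.

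**What to change.** Add a third exception to PKAP 5.2: serial post-dose samples from the PK sub-study are excluded from the sparse-sampling summaries and plots, and each subject contributes at most one sample per visit.

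State also what happens to the pre-dose sample at the profile visit. The morning dose is held until it is drawn, so it is always an end-of-interval value, whereas the sparse samples have no stated time after dose. If it is kept, identify it as a trough and show the cell with and without it. If it is left out, profiled subjects have no value in that cell.

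The cost is a sentence or two in the PKAP and a filter in the program. Serial data remain in the sub-study listings and tables and in the population PK data set. There is one small loss. PKAP 5.1 limits the sub-study population to subjects with adequate profiles and drops those with a pre-dose value below quantification from its summary tables. The serial samples of those subjects would then appear only in listings, and the PKAP should say so.
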